8.6.2 Time to Dose Level increase after the Titration Period

Time to dose level increase after the titration period will be calculated for all subjects. Dose level increase is defined as the first dose level increased from the stable dose to a stable higher dose level. The stable higher dose is defined as an increased dose taken by the subject for at least 2 weeks. The first time when the subject reached the stable higher dose is defined as the date of the dose level increase. The time to dose level increase is calculated as follows:

Date of dose level increase – the stable dose date+ 1.

The visit 10 date in the long term safety will be used as the stable dose date. The time to discontinuation will be estimated using the Kaplan-Meier method. If a subject completed the treatment per the protocol without dose increase (increase to a stable level) will be censored at the date of last dose of treatment.

8.6.3 Time to Discontinuation

Time to treatment discontinuation due to any reason will be calculated for all subjects. The time to discontinuation is calculated as follows:

Date of last dose – date of first dose + 1.

The first dose date is the first titration dose in the long term safety study. The time to discontinuation will be estimated using the Kaplan-Meier method. If a subject completed the treatment per the protocol, the subject will be censored at the date of last dose of treatment. Time to treatment discontinuation due to AE, lack of efficacy, and time to treatment discontinuation due to any reason will be summarized separately.

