Statistical Methods:	
Summaries for the assessment of long-term safety will be presented by De Novo and Rollover Subjects separately and for all subjects combined. The frequency and percentage of subjects experiencing treatment-emergent adverse events (TEAEs), serious adverse events (SAEs), and AEs leading to withdrawal from the study drug will be tabulated by Medical Dictionary for Regulatory Activities (MedDRA) system organ class, preferred term, severity, and relationship to the study drug. Laboratory test results, vital signs, ECGs, SOWS, COWS, and change from baseline will be summarized using descriptive statistics. The relationship between duration of exposure and the frequency and severity of AEs will be examined. Time-to-event endpoints will be estimated using the Kaplan-Meier method. Change over time from baseline in each question and metric of the mBPI-SF will be summarized using descriptive statistics.

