5.3 Removal of Subjects from Study Therapy or Assessment

Subjects may choose to discontinue the study at any time, for any reason, and without prejudice to further treatment.

Subjects may stop participating in or be withdrawn from the study for any of the following reasons but are to be followed for safety until resolution or for 14 days after the subject's last study visit, whichever comes first (see Section 10.1.5):

- Lack of efficacy
- Occurrence of an unacceptable AE
- Opioid withdrawal
- Noncompliance of the subject with protocol-mandated procedures
- Continued participation is no longer in the subject's best interest in the opinion of the Investigator
- The subject is lost to follow-up. Before a subject is considered "lost to follow-up," study personnel must contact the subject at least twice by phone and once by mail with documented receipt(s)
- Death
- The study is terminated by the sponsor

During the treatment period, if an ECG is obtained and reveals that the subject's QTcF interval is > 500 msec or has an increase of ≥ 60 msec compared to baseline QTcF and confirmed with a second ECG within 30 minutes, treatment with study medication should be interrupted. In the event this occurs, the investigator should contact the Medical Monitor as soon as possible to discuss if the subject can continue on treatment or if the subject should stop study medication.

In the event of a subject's withdrawal, the Investigator will promptly notify the sponsor and make every effort to complete the ET assessments specified in the Schedule of Assessments (Section 1.2).

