Subjects will return to the clinic for assessments of tolerability and effectiveness every 4 to 10 days for up to 6 more times over a 5-week period until a stable dose is achieved. A **stable** dose is a dose that is effective and tolerated on two sequential visits (i.e., after at least 8 days of continuous treatment). Subjects who continue to tolerate study drug but do not have adequate relief of pain, based on the Investigator's clinical judgment, will continue dose escalations of 100-mg BID increments until the maximum dose of 600-mg NKTR-181 BID is reached.

Subjects who do not achieve adequate pain control at 600-mg NKTR-181 BID will be classified as non-responders and will be discontinued from further participation in the study.

Non-responders will be required to complete the ET Visit (Visit 21/ET) and safety follow-up requirements.

Subjects will begin a monthly clinic visit schedule after a tolerable, effective and stable dose is achieved. **Doses of NKTR-181 may be adjusted upwards (up to a maximum dose of 600-mg NKTR-181 BID) or downwards as needed during the Treatment Period, based on the Investigator's (or qualified sub-Investigator's) assessment of effectiveness and tolerability.**

If at any time a subject cannot tolerate study drug between protocol-mandated visits, per Investigator discretion, an unscheduled visit should occur. For subjects with tolerability issues, the dose of NKTR-181 may be adjusted downwards, as necessary, based on the Investigator's clinical judgment in a stepwise 100-mg changes (e.g., 300-mg BID may be lowered to 200-mg BID). Dose adjustments may occur at unscheduled visits, however, an unscheduled visit will not replace a regularly scheduled visit, and the subject should be seen at all regularly scheduled visits.

Throughout the Treatment Period, subjects who experience breakthrough pain will be allowed rescue medication, as outlined in Section 6.4. Note: If subject is off of study drug for 3 days or more, sponsor **must** be consulted prior to restarting study drug.

Subjects will report their pain experience at each visit using the mBPI-SF. At quarterly intervals, subjects will be assessed for vital signs, 12-lead electrocardiogram (ECG), and clinical laboratory testing.

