11.9.1 Time to Discontinuation

The time to discontinuation from study drug due to AEs and time to discontinuation due to any reason will be summarized using Kaplan-Meier estimates.

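### Kaplan-Meier is planned for discontinuation due to AE and lack of efficacy with no rule for other exits; if these are censored, 1-KM overstates each cause

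*SAP*

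**What the plan says.** SAP 8.6.3 defines the time variable as "Date of last dose – date of first dose + 1", counted from the first titration dose in this study. On the estimator it says "The time to discontinuation will be estimated using the Kaplan-Meier method", and on censoring only "If a subject completed the treatment per the protocol, the subject will be censored at the date of last dose of treatment". It closes with the list of outcomes: "Time to treatment discontinuation due to AE, lack of efficacy, and time to treatment discontinuation due to any reason will be summarized separately".

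Protocol 11.9.1 covers AE and any reason: "The time to discontinuation from study drug due to AEs and time to discontinuation due to any reason will be summarized using Kaplan-Meier estimates". It does not list lack of efficacy, but the synopsis is general: "Time-to-event endpoints will be estimated using the Kaplan-Meier method".

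The other exits are set out in Protocol 5.3, which begins "Subjects may stop participating in or be withdrawn from the study for any of the following reasons" and lists lack of efficacy, unacceptable AE, opioid withdrawal, noncompliance, investigator judgement, loss to follow-up, death and sponsor termination. Protocol 6.2 adds that subjects without adequate pain control at the maximum dose "will be classified as non-responders and will be discontinued from further participation in the study".

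Neither document mentions competing risks or a cumulative incidence function. SAP 9.0 declares no change from the protocol.

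**The concern.** A subject who has stopped study drug for lack of efficacy can no longer stop it for an AE, and the reverse also holds. These exits are competing events. Kaplan-Meier for one cause, with the other causes censored, treats those who left as if they remained able to have the event. Its complement then describes a hypothetical setting in which the other exits do not occur, not the proportion of dosed subjects who stopped for that cause.

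Long-term tolerability is the primary objective, and a reader will take a 52-week AE-discontinuation curve as the share of subjects who could not tolerate the drug. If the curve is read off as 1-KM, that share could be too high. It would also differ, in the same report, from the percentages tabulated by reason.

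**Working it through.** **Inputs.** The documents supply the estimator, the time variable and the exit reasons, but no expected discontinuation rate and no split by reason. There is therefore no figure in the plan to reproduce. Total exit by Week 52 (T) and the share of exits due to one cause (s) are assumptions, shown as ranges.

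**Step 1: what the time variable implies.** For a subject who leaves for another reason, last dose minus first dose plus 1 ends at that exit, with no AE-discontinuation event. In a Kaplan-Meier analysis of that variable, this is a censored record. Keeping the subject at risk to Day 364 would need a different time variable, which SAP 8.6.3 does not define.

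**Step 2: direction, without assumptions on hazards.** At each event time, cause-specific Kaplan-Meier adds (cause-specific survival just before) × (events / at risk). Aalen-Johansen adds (all-cause survival just before) × (the same fraction). All-cause survival is never the larger of the two, so 1-KM is never below the cumulative incidence. It is above it once a competing exit precedes an event.

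**Step 3: size under proportional cause-specific hazards.** With H = -ln(1 - T):

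- cumulative incidence = s × T
- 1-KM = 1 - exp(-sH) = 1 - (1 - T)^s

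Example with T = 50% and s = 30%: cumulative incidence = 0.30 × 0.50 = 15.0%; 1-KM = 1 - 0.5^0.3 = 18.8%; gap 3.8 points.

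Cumulative incidence vs 1-KM at Week 52, gap in points:

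| T | s = 15% | s = 30% | s = 50% |
|---|---|---|---|
| 20% | 3.0% vs 3.3% (0.3) | 6.0% vs 6.5% (0.5) | 10.0% vs 10.6% (0.6) |
| 30% | 4.5% vs 5.2% (0.7) | 9.0% vs 10.1% (1.1) | 15.0% vs 16.3% (1.3) |
| 40% | 6.0% vs 7.4% (1.4) | 12.0% vs 14.2% (2.2) | 20.0% vs 22.5% (2.5) |
| 50% | 7.5% vs 9.9% (2.4) | 15.0% vs 18.8% (3.8) | 25.0% vs 29.3% (4.3) |
| 60% | 9.0% vs 12.8% (3.8) | 18.0% vs 24.0% (6.0) | 30.0% vs 36.8% (6.8) |

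**Step 4: additivity.** Split T = 50% into AE 30%, lack of efficacy 20% and all remaining reasons 50%. The three 1-KM values are 18.8%, 1 - 0.5^0.2 = 12.9% and 1 - 0.5^0.5 = 29.3%. They sum to 61.0%, against 50% for any reason. The SAP plans the first two curves; the third is the implied remainder.

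**Step 5: early AE exits.** Titration makes early AE exits plausible. A simulation used 600 subjects (the planned number, Protocol 11.2), 40 replicates per T, and the same 30/20/50 split. About 70% of AE exits fell in Days 1-56 and the rest in Days 57-357; lack-of-efficacy exits were spread over Days 28-357 and other exits over Days 1-357.

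| T | AE: cumulative incidence vs 1-KM | Lack of efficacy | Sum of three 1-KM values |
|---|---|---|---|
| 40% | 12.0% vs 13.0% | 8.0% vs 10.2% | 46.4% |
| 50% | 15.0% vs 16.6% | 10.0% vs 13.8% | 60.8% |

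Early events are inflated less because fewer competing exits precede them. Later lack-of-efficacy events are inflated more.

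**Step 6: the alternative handling.** In the same simulation, keeping other-cause exits at risk to Day 364 made 1-KM for AE equal the cumulative incidence (12.0% and 12.0% at T = 40%). The overstatement therefore depends entirely on how other exits are handled.

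**The case against.** A reader might infer that the plan is wrong as written and that its AE figure will be biased upward. The documents do not support that much. The censoring rule concerns completers only; censoring of other exits is inferred from the time variable and usual practice. Nor does any section say that 1-KM will be reported as the risk of stopping for a cause. Cause-specific Kaplan-Meier is a legitimate description of net risk if censoring is independent, although the SAP does not claim that estimand.

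The strongest further point is that the right Week 52 figure is largely planned already. SAP 8.1 summarizes reasons for early discontinuation, and SAP 8.7.1 gives the number and percentage with AEs that led to study drug withdrawal. All dosed subjects have the same 52-week horizon, and loss to follow-up and sponsor termination are themselves listed exit reasons. The cumulative incidence at Week 52 is therefore approximately the number stopping for the cause divided by the number dosed. This stands. What the cumulative incidence curve adds is the course before Week 52, an interval, and agreement with those tables.

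It is also true that time to discontinuation is not among the key safety endpoints, that the study is single-arm with no test or threshold tied to this curve, and that an overstated AE risk errs on the cautious side.

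A second tempting inference takes the target of at least 100 subjects completing 52 weeks as a forecast. Out of 600 that would mean 500/600 = 83.3% exit and, at s = 30%, 41.6% by 1-KM against 25.0%. The target is an exposure minimum, not an expected completion rate, so this gap is only an outer case.

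**Conclusion.** The gap in the plan is real: Kaplan-Meier is named for cause-specific discontinuation, competing exits are certain to be possible, and their handling is not stated. If they are censored at last dose, as the time variable implies, 1-KM overstates the cumulative incidence of AE and of lack-of-efficacy discontinuation. The cause-specific values would then sum to more than the any-reason curve and would not match the crude percentages by reason.

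The direction rests only on that handling. The size rests on assumed attrition, shares and proportional hazards: under 1 point at 20% total exit, roughly 1.5 to 2.5 points at 40% and 2.5 to 4.5 at 50%, with a smaller gap for AE if those exits come early. The any-reason curve is correct as planned. This is a worthwhile improvement to a descriptive analysis; it does not undermine the study's safety assessment.

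**What to change.** In SAP 8.6.3:

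- Keep Kaplan-Meier for discontinuation due to any reason.
- For AE and for lack of efficacy, report the Aalen-Johansen cumulative incidence with 95% CI. Treat every other discontinuation reason as a competing event and censor completers at last dose.
- If a net-risk Kaplan-Meier curve is also wanted, label it as such and state that other exits are censored and assumed independent.

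Because Protocol 11.9.1 names Kaplan-Meier for AE discontinuation, SAP 9.0 should record the change.

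The cost is a few lines of SAP text and a small amount of programming with a standard method, using reason and last-dose data already collected. The cause-specific figures will be slightly lower than 1-KM would give, and they will agree closely with the crude tables at Week 52.

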8.6.4 Rescue Medication

A subject's rescue medication use will be calculated based on drug accountability recorded in CRF. The mean number of occasions rescue medication per day will be presented by dose level

using descriptive statistics. The mean number of occasions rescue medication per day will be derived for each visit, if appropriate, as well as overall. The frequency of subjects using any rescue medication in terms of mean number of occasions rescue medication per day will be summarized by dose level by visit as well as overall.

The mean number of occasions rescue medication per day will be calculated as follows:

$$\frac{\text{(sum of number of occasions of rescue medication)}}{\text{(exposure duration of study drug in days)}}$$

The number of rescue medication taken based on drug administration will be calculated as the total number of tablets dispensed minus the total number of tablets returned. If the number of returned tablets is missing, it will be assumed that the subject took the dispensed all tablets during that visit. For those subjects who are lost to follow-up, it will be assumed that they took the number of prescribed tablets up until the last day of contact.

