6.4 Rescue Medication

Nektar will provide over-the-counter analgesics, including aspirin, acetaminophen, ibuprofen, and naproxen, for subjects who experience breakthrough pain. The subject, in consultation with the Investigator, will be allowed to choose which rescue medication(s) they will use. Subjects may use their selected rescue medications up to the maximum daily dose indicated on the label, at any time during the study.

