7.1.2 Rescue Medication

For subjects who are experiencing breakthrough pain, the sponsor will provide aspirin, acetaminophen, ibuprofen, and naproxen for use as rescue medication. Aspirin will be provided in 325-mg tablets for oral use. Acetaminophen will be provided in 500-mg tablets for oral use. Ibuprofen will be provided in 200-mg tablets for oral use. Naproxen will be provided in 220-mg tablets for oral use, as directed on label.

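### The rescue summary in SAP 8.6.4 is labelled in occasions per day, but its only named source is tablet counts, which cannot yield occasions

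*SAP*

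**What the plan says.** SAP 8.6.4 (Rescue Medication) names one data source: "A subject's rescue medication use will be calculated based on drug accountability recorded in CRF". The statistic is then named: "The mean number of occasions rescue medication per day will be presented by dose level". Its formula has the numerator "sum of number of occasions of rescue medication" and the denominator "exposure duration of study drug in days". The value is to be derived overall and, where appropriate, for each visit. A count of subjects with any rescue use is also planned.

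The only rule for the amount taken is a tablet count: "The number of rescue medication taken based on drug administration will be calculated as the total number of tablets dispensed minus" the tablets returned. Two gap-filling rules follow:

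- For missing returns: "If the number of returned tablets is missing, it will be assumed that the subject took the dispensed all tablets during that visit".
- For subjects lost to follow-up, the tablets *prescribed* up to last contact are assumed taken.

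Protocol 7.1.2 lists four products. The first two read: "Aspirin will be provided in 325-mg tablets for oral use. Acetaminophen will be provided in 500-mg tablets for oral use". The others are ibuprofen 200 mg and naproxen 220 mg. Under Protocol 6.4 the subject, in consultation with the investigator, chooses one or more of these and may use them "at any time during the study". Protocol 7.4 describes accountability as unit counts of returned medication. Protocol 11.8 asks only for a descriptive summary of rescue use over time.

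**The concern.** The label and the derivation describe different quantities. An occasion is an act of taking rescue; a unit count shows how many tablets left the supply between visits. The count does not say whether 30 missing tablets were 30 single-tablet occasions or 15 two-tablet occasions.

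This matters for reading the pain results. The mBPI-SF is the secondary objective, and neither the MMRM in SAP 8.6 nor the responder rates in SAP 8.6.1 make any allowance for rescue. The rescue table is therefore part of the context a reader will use. If its figures are tablets headed as occasions, dose levels could appear to differ in how often subjects needed rescue when they differ only in tablets per occasion or in choice of product.

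Two further gaps sit in the same section: no statement on whether products are combined, and no denominator suited to a per-visit value.

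**Working it through.** The documents give no numeric rescue figure, so there is none to reproduce. The check compares the text of the sections and then illustrates the sizes. Every assumed value is marked.

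**1. Can the numerator be obtained from the named source?** The formula needs occasions. The source is accountability (SAP 8.6.4), which yields unit counts (Protocol 7.4). SAP 8.6.4 neither defines an occasion nor converts tablets to occasions, and the protocol describes no rescue diary or intake-time record. The concomitant medication eCRF (Protocol 6.6) records dose and dosing frequency, but SAP 8.6.4 does not name it. The numerator cannot be derived as specified.

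**2. If the tablet count is used as the numerator:**

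(dispensed − returned) ÷ days = (occasions per day) × (tablets per occasion)

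This takes every unreturned tablet as swallowed. Tablets per occasion is an assumption, varied from 1 to 3:

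| True occasions per day (assumed) | 1 tablet each | 2 tablets each | 3 tablets each |
|---|---|---|---|
| 0.5 | 0.5 | 1.0 | 1.5 |
| 1 | 1.0 | 2.0 | 3.0 |
| 2 | 2.0 | 4.0 | 6.0 |

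The ratio to true occasions is simply the number of tablets per occasion: 1.0, 2.0 or 3.0.

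**3. What does one tablet represent?** From Protocol 7.1.2: ibuprofen 200 mg, naproxen 220 mg, aspirin 325 mg, acetaminophen 500 mg. The range is 500 ÷ 200 = 2.5-fold in mg, across different drugs for which mg are not interchangeable. A pooled count would vary with product mix.

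**4. Per-visit denominator.** The only denominator is study-drug exposure duration, which SAP 8.5 defines as last dose date − first dose date + 1. Take 30 tablets used over one 30-day visit interval (the spacing in Protocol 1.2):

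- over the interval: 30 ÷ 30 = 1.0 per day;
- over a full 52 weeks (364 days), if the formula is read literally: 30 ÷ 364 = 0.08 per day, about 12 times lower (364 ÷ 30 = 12.1).

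A programmer would probably not do the second, but the SAP gives no alternative.

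**5. Missing returns.** Pack size is not stated. With an assumed 24, 50 or 100 tablets dispensed for 30 days, the full-use rule gives 24 ÷ 30 = 0.80, 50 ÷ 30 = 1.67 or 100 ÷ 30 = 3.33 per day, whatever was actually taken.

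**6. Lost to follow-up.** SAP 8.5 uses *dispensed* tablets in the matching rule for study drug; SAP 8.6.4 uses *prescribed* tablets. Rescue is taken as needed, so no prescribed number exists to insert.

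**The case against.** A reader might draw several stronger conclusions that the documents do not support.

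- **That the SAP equates occasions with tablets.** It does not. The numerator is worded as occasions, and the tablet rule is a separate sentence. The link is an inference from there being one source and one derivation. This stands as a limit: the defect is a missing definition and conversion rule, not a demonstrated miscalculation.
- **That the four products are summed together.** The SAP is silent on this, and an individual subject may use only one product. The gap is the silence.
- **That the statistic is overstated by a known factor.** The ratio only restates the assumed tablets per occasion, and at one tablet there is no error.
- **That tablets from the screening taper inflate the numerator.** Protocol 6.1.2 allows rescue during the De Novo taper, but nothing says those tablets are counted. In Protocol 1.2 the study-drug dispensing and collection row starts at Visit 3, and final rescue reconciliation is at Visit 22. A mismatch is possible but not shown.
- **That counting a missing return as full use is an error.** It is a stated convention, and SAP 8.5 applies it to study drug too. Dropping those intervals has its own cost, since failed accountability may not be random.

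The concomitant medication form might supply frequency data, and the CRF pages are not available to check. That suggests a possible remedy, but the section as written does not use that form. It is also fair that rescue use is not a listed endpoint, that adjuvant analgesics are permitted as well, and that a summary of any use is already planned.

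**Conclusion.** The point holds in limited form. SAP 8.6.4 promises a quantity that its named source cannot supply. A tablet count in its place would match the label only if every occasion were a single tablet. Handling of the four products is unspecified, the per-visit value lacks an interval denominator, and the lost-to-follow-up rule rests on an undefined quantity.

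No corrected value can be computed from the documents. The ratios of 1.0 to 3.0 and the missing-return figures rest on assumed tablets per occasion and pack sizes. The split between any use and no use does not depend on tablets per occasion, though it does depend on the missing-return rule. The effect is confined to a descriptive summary: sample size and the primary safety objective are untouched. This is a minor but clear specification fault, best corrected before the tables are programmed.

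**What to change.** In SAP 8.6.4:

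1. Rename the statistic tablets per day (or mg per day) and report it separately for each of the four products.
2. For per-visit values, divide by the days in that dispensing interval that fall within the study-drug exposure period. Keep exposure duration for the overall value.
3. Keep the planned summary of subjects with any rescue use.
4. Keep the full-use rule for missing returns, report how many intervals it affects, and add a sensitivity summary without them.
5. For subjects lost to follow-up, replace prescribed tablets with a rule based on dispensed tablets, in line with SAP 8.5.

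If occasions are really wanted, the alternative is to define an occasion and name a data source that records it.

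The recommended route uses the accountability counts, provided they are held by product. It costs a revised paragraph, new table labels and one small sensitivity table.
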